5. Down-selection of the final vaccine regimen for PfSPZ Vaccine and ongoing studies: The Day 1, 8 and 29 day regimen shown in the MAVACHE trial in Germany to provide >80% protection against heterologous CHMI at 3 and 10 weeks after immunization has been selected as the optimal regimen, combining high-level protection with a practical 3-dose, 4-week administration schedule. All the most recent trials – #16 to #22 in **Table 4** – assess this regimen. The results from the EGSPZV3 trial are recently available and indicate that the Day 1, 8 and 29 regimen was the most protective of the four regimens tested [43]. The study underway in 6-10-year-old Malian children (#21 in **Table 4**) and the study underway in Indonesian soldiers (#22 in **Table 4**) are using the same Day 1, 8 and 29 regimen, and are measuring VE against naturally transmitted malaria. Likewise, the Warfighter 3 trial in Seattle (#20 in **Table 4**) is testing the same regimen against CHMI, with results expected soon.
6. Rationale for the USSPZV7 trial: The USSPZV7 trial is designed to help link the results of these various trials. Together with Warfighter 3, USSPZV7 will allow bridging of VE data between malaria-naive and malaria-exposed individuals as illustrated in **Table 6**.

Table 6. Linked studies using the Day 1, 8 and 29 regimen

Population	Malaria-naive adults		Malaria-exposed adults
VE measurement	CHMI	naturally transmitted Pf	naturally transmitted Pf
Gender	50% male / 50% female	100% male (soldiers)	100% female (women of child-bearing potential)
Trial location	US	Indonesia	Mali
Name	USSPZV7	IDSPZV1	MLSPZV4

A comparison of USSPZV7 and IDSPZV1 will tell us how protection against CHMI translates into field efficacy in the same malaria-naive population (relying on males), and a comparison between TravSPV1 and MLSPZV4 will tell us how protection against CHMI in a malaria-naive population translates into field efficacy in a malaria-exposed population (relying on females). The Warfighter 3 trial will provide similar information using different intervals to heterologous CHMI (2, 6 and 10 weeks) compared to USSPZV7 (3 and 12 weeks).

3. *Studies using PfSPZ Challenge to assess vaccine efficacy:* There have been 17 trials wherein PfSPZ Challenge (NF54) has been used to assess VE. These assessed the VE of PfSPZ-CVac, the vaccine candidate GMZ2, and PfSPZ Vaccine (**Table 4**: Trials # 5, 8, 9, 13, 14, 15, 18) [4, 31, 32, 38, 40]. Using PfSPZ Challenge to assess efficacy is convenient because timing is not dependent on the development of a batch of infected mosquitoes, the dose is standardized, and the cost is considerably less than mosquito bite CHMI. These features have allowed the first modern CHMI's in Africa, and to date these have been performed in six African countries.

The clinical trials described above used Pf Challenge (NF54), which is composed of the same strain of Pf as PfSPZ Vaccine. PfSPZ Challenge (Pf7G8) has been developed more recently to provide heterologous CHMI, a more stringent assessment of VE. PfSPZ Challenge (7G8) contains a cloned parasite from Brazil which is heterologous (genetically and antigenically) from PfNF54. The trials with PfSPZ Challenge (Pf7G8) are discussed below.

2.1.5.3 CLINICAL INVESTIGATIONS USING PFSPZ CHALLENGE (7G8)

1. MAVACHE Trial: This was a Phase 1 sequential dose and schedule optimization trial primarily designed to assess the safety, tolerability and efficacy of PfSPZ Vaccine. However, a component of the trial consisted of a small dose escalation study of PfSPZ Challenge (7G8), performed in healthy, malaria-naïve participants, to establish the minimum 100% infective dose. DVI of 3,200 PfSPZ was fully infective in this small trial, while lower doses were not. Thus PfSPZ (Challenge 7G8) infectivity appeared similar to that of PfSPZ Challenge (NF54). PfSPZ Challenge (7G8) was subsequently used in the MAVACHE trial to assess heterologous protection induced by PfSPZ Vaccine [32].
2. NIAID sponsored trial 14-0040 at University of Maryland: This randomized, double-blind Phase 1 trial of DVI of PfSPZ Challenge (7G8), with PfSPZ Challenge (NF54) used as a comparator, had a similar objective to the 7G8 component of the MAVACHE trial: dose escalation of PfSPZ Challenge (7G8) to establish the minimum 100% infective dose. As with MAVACHE, the trial was done in non-immune adults and assessed the safety and reactogenicity of PfSPZ Challenge (7G8) administered by DVI. The CHMI was safe and well tolerated and yielded the following infectivity results: 800 PfSPZ: 3/7 infected; 1600 PfSPZ: 4/7 infected; 3,200 PfSPZ: 8/9 infected; 4800 PfSPZ: 2/2 infected [30]. On the basis of the results of MAVACHE and NIAID 14-0040, 3,200 PfSPZ was selected as the standard dose, the same as for PfSPZ Challenge (NF54), although there was one participant in the University of Maryland trial who did not become positive at this dose.
3. Protocol 17-I-0067 trial in the US and TÜCHMI-003 trial in Germany: Subsequent to these two dose optimization trials, PfSPZ Challenge (7G8) has been used to assess VE in two trials in addition to the MAVACHE trial: the 17-I-0067 PfSPZ-CVac (pyrimethamine) trial at the NIH Clinical Center [54], and the

TÜCHMI-003 trial in Tübingen, Germany [31]. The product was safe and well tolerated in all research participants injected, and as with MAVACHE, all controls inoculated with 3,200 PfSPZ became infected. In total, 27/28 malaria-naïve individuals undergoing CHMI with PfSPZ Challenge (7G8) using 3,200 PfSPZ administered by DVI have turned positive.

In summary, PfSPZ Challenge (7G8) is available as a standardized method for CHMI that is safe, well tolerated, consistently infectious, and allowing flexibility with respect to the timing of inoculation. When used to assess the efficacy of PfSPZ Vaccine, it provides a heterologous CHMI, increasing stringency and better representing the heterogeneous population of parasites found in nature, almost all of which will be different from NF54. In two comparisons where precisely the same regimen was tested in Malian adults against naturally transmitted malaria over a 24 week surveillance period and in US adults against PfSPZ Challenge (7G8) CHMI conducted 24 weeks after immunization, protection was as high or higher in the field than following heterologous CHMI [33]. CHMI with PfSPZ Challenge (7G8) should thus provide a conservative estimate of “real world” protection in the field.

2.2 RISK/BENEFIT ASSESSMENT

2.2.1 KNOWN POTENTIAL RISKS

2.2.1.1 RISK ASSOCIATED WITH PFSPZ VACCINE

2.2.1.1.1 LOCAL REACTIONS

PfSPZ Vaccine will be administered by DVI. In the DVI procedure, a small-bore (25 gauge) needle is inserted into the vein, the syringe plunger is withdrawn slightly to demonstrate blood flashback, and the vaccine injected directly, a procedure lasting <10 seconds once the skin has been prepped with alcohol. The procedure has been extremely well tolerated. This is likely due to the small needle (the trauma of penetration is minimized) and the fact that with intravascular injection there is no depot of fluid forced into a tissue space as with other routes of injection.

The local risks of PfSPZ Vaccine administered by DVI include pain, tenderness, erythema, swelling, bruising, pruritus and induration. Additional, less common risks associated with venipuncture are listed in Section 2.2.1.4 ‘Risk Associate with Venipuncture’.

2.2.1.1.2 SYSTEMIC REACTIONS

PfSPZ Vaccine has been exceptionally safe and well tolerated in malaria-naïve adults in the US and Europe, and in malaria-exposed adults, children and infants in Africa. In these trials, as of 18 July 2022, 6255 doses of PfSPZ Vaccine (over 5.7 billion PfSPZ) have been safely injected into 1981 participants aged 5 months to 65 years in Tanzania, Kenya, Mali, Burkina Faso, Gabon, Equatorial Guinea, Germany, the Netherlands and the US, including 873 doses administered by DVI to 330 infants.

An early safety concern with PfSPZ Vaccine was breakthrough malaria infections due to inadequate attenuation. However, there have been no observed breakthroughs following injection with over 5,000 doses of PfSPZ Vaccine administered to date. A second concern had been local side effects at the injection site, given the reactogenicity of mosquito bites and the possibility that sporozoites may contribute. Interestingly, there appears to be little or no local reactogenicity associated with PfSPZ injection: in trials of attenuated sporozoite

immunization by mosquito bite, the papules, edema, erythema and pruritus induced were equivalent between true immunization using infected mosquitoes and mock immunization using non-infected mosquitoes, indicating that mosquito saliva must be the cause [55]. Additional information comes from trials of PfSPZ Vaccine and PfSPZ Challenge injected ID and SC. These routes of administration leave a depot of PfSPZ in or under the skin, but do not cause local inflammation at the injection site, even after repeated dosing [36]. The manufacturing process at Sanaria removes nearly all mosquito components, explaining the apparent absence of reactogenicity.

The third concern has been that PfSPZ Vaccine might cause systemic reactogenicity. In all trials so far, the majority of vaccine recipients reported no or mild systemic AEs, with only a few classified as moderate in severity. Fever has only rarely been reported as a solicited AE and the few reports to date were generally attributed to other causes. There also did not appear to be an increase in adverse events with repeated dosing (i.e., the rate of adverse events after second or third doses compared to the rate after first dose). In addition, there have been no allergic reactions clearly linked to the vaccine. The overall side effect profile appears to be nil, with no differences identified between vaccinees and normal saline controls in eight randomized, double-blind, placebo-controlled trials with respect to solicited adverse events, unsolicited adverse events, or laboratory abnormalities. PfSPZ Vaccine, which is formulated without an adjuvant, has appeared to be one of the least reactogenic vaccines ever assessed in clinic trials.

One safety question not yet fully resolved is the adverse event profile of condensed regimens. For example, if the second dose of vaccine is given 7 days after the first dose, rather than the 4 to 8 weeks after the first dose, is there increased reactogenicity? Data from the MAVACHE trial in Germany indicate that this might be the case at the higher doses tested in that trial. In the group (n=6) that received 9×10^5 PfSPZ per dose on Days 1, 8 and 29, these systemic reactions were not observed. However, higher doses of the condensed regimens were associated with systemic symptoms when the second dose was given on Day 8. In the group receiving 1.35×10^6 PfSPZ on Days 1 and 8, 4/6 participants had systemic symptoms following the second immunization of the vaccine. Symptoms occurred approximately 10-12 hours after administration on the same day in three volunteers and approximately 24 hours after administration on the next day in another volunteer. These symptoms included fever, chills, sweats and fatigue that were Grade 1 in severity. One participant had additional symptoms of Grade 1 diarrhea, arthralgia, myalgia and abdominal pain. All four participants experienced headache (Grade 1 in two participants and Grade 2 in two participants). In the group receiving 2.7×10^6 PfSPZ on Days 1 and 8, 1/6 participants experienced Grade 3 fever, chills, sweating, myalgia, fatigue and vomiting the evening of the day of the second immunization, symptoms which lasted about one day.

A frequent laboratory observation in the MAVACHE trial was lymphopenia one day following immunization. There were transient decreases one day after the second dose in all groups. For the group which received 3 doses (9×10^5 PfSPZ on Days 1, 8 and 29), lymphopenia was also observed after the third dose (Grade 1 to 2 in severity). The lymphopenia resolved within approximately one day. Although not well understood, it is hypothesized that the transient lymphopenia may reflect white blood cells migrating to target organs such as the liver to respond to invading parasites.

The dose of PfSPZ planned for USSPZV7 – 9.0×10^5 PfSPZ, is lower than the doses in MAVACHE where adverse events were observed after the second immunization. Such adverse events have not been observed in the pediatric trial in Gabon where the same vaccination regimen as planned for USSPZV7 was used in children age 1 to 12 years. Although the data are still blinded, the combined (vaccine + placebo) adverse event data do not

indicate any concerns. **Table 7** and **Table 8** provide data on solicited adverse events and laboratory abnormalities, respectively, from the LaSPZV1 trial in Gabon.

Table 7. Solicited adverse events recorded days 0-7 post-all immunizations.

Participants received three doses weeks 0, 1 and 4 of 9.0×10^5 PfSPZ of PfSPZ Vaccine. Data from vaccine and normal saline placebo groups combined (trial remains blinded). Data are the number of participants experiencing the AEs.

AE	Severity	1-2 years (n=36)	3-6 years (n=101)	7-12 years (n=63)
Fever (objective)	Mild (38-38.4°C)	3	1	3
	Moderate (38.5-38.9)	1	4	1
	Severe ($\geq 39.0^{\circ}\text{C}$)	1	1	0
poor feeding	Mild	2	1	not applicable
fever (subjective)	Mild	not applicable	1	
	Moderate		2	
chills	Mild		1	
fatigue	Mild		3	
	Moderate		3	
headache	Mild		8	
	Moderate		2	
arthralgias	Mild		0	
	Moderate		1	
myalgias	Mild		0	
	Moderate		1	

Subjective fever: parent's impression that child had fever within past 24 hours.

Children aged 1-6 were scored with regard to inability to eat, drowsiness and irritability /fussiness; there were no instances of drowsiness or irritability/fussiness.

Children aged 7-12 were questioned with respect to solicited symptoms. There were no recorded instances of malaise. In all three age groups, there were no findings suggestive of an allergic reaction, including rash, urticaria, pruritis, or edema.

Table 8. Laboratory abnormalities Grade 2 or higher by age group, days 1 to 28 post-immunization.

Tests were scheduled 1 and 7 days after each vaccine dose and prior to V3. The table also includes any unscheduled lab tests. Data are from vaccine and normal saline placebo groups combined (trial remains blinded). Data are the number of participants experiencing the abnormalities and also the number of abnormalities experienced (no child had more than one lab abnormality of a given type).

Laboratory abnormality	Severity Grade	1-2 years (n=36)	3-6 years (n=101)	7-12 years (n=63)
ALT elevation	Grade 2 or higher	0	0	0
Creatinine elevation	Grade 2	0	0	1
	Grade 3 or higher	0	0	0
Hemoglobin decrease	Grade 2 or higher	0	0	0
WBC decrease	Grade 2 or higher	0	0	0
Platelet count decrease*	Grade 2	0	0	1
	Grade 3	1	2	0
	Grade 4	0	0	1

[figure not shown]
*All Grade 3 and 4 platelet count abnormalities occurred 1 day after immunization (two episodes with dose 1, 1 with dose 2, 1 with dose 3). Preceding values normal in all cases. Follow-up tests also normal in all cases, performed after 4 days (Grade 3), 5 days (Grade 3 and Grade 4), 6 days (Grade 3) and 21 days (Grade 2). There were no repeat episodes of decreased platelet counts with subsequent dosing. Toxicity scale criteria: Grade 2 creatinine elevation: > 88-141 μ mol/L; Grade 2 platelet count: 51-75,000/ μ L Grade 3 platelet count: 25-50,000/ μ L; Grade 4 platelet count: < 25,000/ μ L

These findings in pediatric studies are illustrative of the findings in all trials of PfSPZ Vaccine, including all twelve randomized, double-blind, normal saline placebo-controlled trials that have been completed and unblinded. None of these trials has shown any differences in the rates of any AEs between vaccine recipients and controls after unblinding that have achieved statistical significance (#4, 5, 7-10, 12, 14-16, 18-19 in **Table 4**) [2, 4, 38-43, 56, 57] except for one study where there was an excess of myalgia in the vaccine group (#10 in **Table 4**). Most importantly, there were no age or dose effects on the rates of AEs with doses as high as 1.8×10^6 PfSPZ in infants and young children [40, 41]. It is thus not clear that PfSPZ Vaccine has consistently caused *any* adverse reactions, other than the anecdotal data from the high doses administered in the MAVACHE trial.

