in the KSPZV1 trial in Kenya (#12 in **Table 4**). Although many infants experience febrile seizures in association with malaria or other infections in that trial, these febrile seizures were expected adverse events not linked to immunization. It was noted that epilepsy was diagnosed in several children during the KSPZV1 trial, at a frequency not statistically different from the known background rate of epilepsy in the same population. Until larger numbers of children have received PfSPZ Vaccine, Sanaria recommends excluding any individuals with a history of non-febrile seizures from participation in clinical trials of PfSPZ-based products, although with further clinical experience this restriction may be lifted. This exclusion applies to the USSPZV7 trial.

Although the data indicate that PfSPZ Vaccine does not cause adverse reactions at the doses planned for this study, nevertheless the consent form lists the following reactions any vaccine might theoretically cause, including: objective fever (oral temperature $> 100.4^{\circ}$ F), subjective fever, chills, headache, fatigue, malaise, myalgia, arthralgia, rigors, and systemic reactions that might indicate allergic responses (rash, urticaria, pruritus, and edema); these will constitute the list of solicited adverse events which are assessed after each immunization. Additional risks are abnormal laboratory tests, including elevated liver function tests and transient changes in blood counts. Because the vaccine is administered by DVI into a superficial vein, the participant is also at risk of having a vasovagal response.

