8.3.1.1 SOLICITED AND UNSOLICITED ADVERSE EVENTS

8.3.1.1.1 SOLICITED ADVERSE EVENTS

A solicited AE is a pre-specified sign or symptom which reflects safety concerns related to the investigational product or procedures. Solicited and unsolicited AEs will be systematically collected in this protocol to measure the safety and tolerability of PfSPZ Vaccine, normal saline and PfSPZ Challenge. Solicitation of local and systemic AEs with respect to each injection will begin after injection of study product. To collect solicited AEs, a specific list of symptoms will be reviewed with the participant face-to-face or via telephone, or specific signs will be identified by physical examination. This approach assures systematic and comprehensive collection of AE data. Trial participants may use a memory aid to help with remembering the AEs they have experienced.

PfSPZ Vaccine or Normal Saline Placebo

Solicited Local AEs (collected for 2 days after each immunization): pain, tenderness, erythema, swelling, bruising, pruritus and induration.

Solicited Systemic AEs (collected for 7 days after each immunization): Fever (oral temperature $\geq 100.4^{\circ}\text{F}$), subjective fever, chills, headache, fatigue, malaise, myalgia, arthralgia, rigors, systemic allergic type reactions (rash, urticaria, pruritus, edema).

PfSPZ Challenge (7G8)

Solicited Local AEs (collected for 2 days after PfSPZ Challenge – CH to CH+2): pain, tenderness, erythema, swelling, bruising, pruritus and induration.

Solicited Systemic AEs (collected for 6 days after PfSPZ Challenge – CH to CH+6): Fever (oral temperature $\geq 100.4^{\circ}\text{F}$), subjective fever, chills, headache, fatigue, malaise, myalgia, arthralgia, rigors, systemic allergic type reactions (rash, urticaria, pruritus, edema).

8.3.1.1.1.1 UNSOLICITED ADVERSE EVENTS

Unsolicited adverse events will be identified through open-ended questions such as "do you have any other symptoms?" This will be asked to prompt the identification of unsolicited adverse events after

reviewing the solicited adverse event list, or as the sole means of collecting adverse event data during visits when solicited adverse events are not being collected.

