A syndromic classification will be used for unsolicited adverse events; e.g., cough, nasal congestion, sore throat will be combined and recorded as “upper respiratory tract infection.” Thus, whenever applicable, the term for the unifying diagnosis will be recorded as the adverse event, not each individual sign or symptom.

Any event not included under the specific list for solicited local or systemic adverse events (see Section 8.3.1.1.1 ‘Solicited Adverse Events’) or malaria events (see Section 8.3.1.2 ‘Malaria Events’ below) will be captured as an unsolicited AE if the AE occurs within 28 days after immunization or CHMI. Events outside of this period will be collected as clinical events.

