8.3.1.2 MALARIA EVENTS

Starting at 7 days post-CHMI through either 28 days post-CHMI (CH+7 to CH+28) or 3 days after treatment commences for parasitemia, participants will be monitored for signs and symptoms consistent with malaria infection. These “Malaria Events” will be documented but will not be categorized as adverse events since they are expected outcomes of malaria infection.

Malaria Events (collected day CH+7 and onward during CHMI): Fever (oral temperature $\geq 100.4^{\circ}\text{F}$), subjective fever, chills, headache, fatigue, malaise, myalgia, arthralgia, rigors, sweats, cough, nausea, vomiting, dizziness, abdominal pain, diarrhea, chest pain, palpitations, shortness of breath, and tachycardia.

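### The solicited list used after each immunization leaves four of the ten symptoms reported after a Day 8 second dose to open-ended reporting; this weakens per-symptom rates, not the participant-level safety count

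*Combined protocol and SAP*

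**What the plan says.** Section 2.2.1.1.2 reports what followed a Day 8 second dose in a previous trial of condensed regimens (MAVACHE). In the 1.35 × 10^6 group, 4 of 6 participants reacted: "These symptoms included fever, chills, sweats and fatigue that were Grade 1 in severity". It adds: "One participant had additional symptoms of Grade 1 diarrhea, arthralgia, myalgia and abdominal pain" and "All four participants experienced headache (Grade 1 in two participants and Grade 2 in two participants". In the 2.7 × 10^6 group, "1/6 participants experienced Grade 3 fever, chills, sweating, myalgia, fatigue and vomiting the evening of the day of the second immunization". In the group of 6 given this trial's dose and schedule, these reactions did not occur. The same section reports transient lymphocyte decreases one day after the second dose in all groups.

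The systemic events solicited for 7 days after each vaccine or saline dose (Section 8.3.1.1.1) are measured fever and "subjective fever, chills, headache, fatigue, malaise, myalgia, arthralgia, rigors, systemic allergic type reactions (rash, urticaria, pruritus, edema". Section 8.1.4 gives the same list. So does the end of Section 2.2.1.1, which says of it that "these will constitute the list of solicited adverse events which are assessed after each immunization". Sections 8.2.1.4 and 8.3.1.1.1 apply this list for 6 days after PfSPZ Challenge as well.

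Anything not on the list is found by an open question and recorded as an unsolicited event if it falls within 28 days. Where a diagnosis applies, "the term for the unifying diagnosis will be recorded as the adverse event, not each individual sign or symptom" (Section 8.3.1.1.1.1). From CHMI+7 the malaria list includes "rigors, sweats, cough, nausea, vomiting, dizziness, abdominal pain, diarrhea" (Section 8.3.1.2).

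**The concern.** Safety and tolerability of the Day 1, 8 and 29 regimen is a primary objective, and the protocol itself says that the effect of the short first interval is not settled. A solicited list would be expected to cover the symptoms that raised the question. This one leaves out sweats, which were named in both reacting groups; vomiting, which was part of the only Grade 3 reaction; and diarrhea and abdominal pain. No reason is given.

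The protocol treats these four symptoms differently elsewhere. Section 2.2.1.2.2 includes all four among the vaccine-type reactions that could follow PfSPZ Challenge before malaria can appear. Section 8.3.1.2 solicits all four from CHMI+7. Section 2.2.1.1.3 says that some previous trials solicited nausea/vomiting, abdominal pain and diarrhea after vaccination.

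At stake is the symptom profile. Section 9.4.4 analyses solicited systemic events one by one and as a total. The four symptoms would be missing from that total, and their individual rates would depend on what an open question brings up and on whether the symptom or a diagnosis is written down. Comparison with trials that solicited them would also be weaker.

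**Working it through.** The plan gives no figure for how well its list covers the previous signal. Its one tolerability calculation (Section 9.2) concerns participant-level proportions and does not bear on which symptoms are asked about. The check is therefore a comparison of lists, followed by a participant count.

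**Step 1: symptoms.** Reported symptoms and grades are from Section 2.2.1.1.2.

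| Symptom | Reported in group (× 10^6) | Highest grade | Solicited after each dose (8.1.4, 8.3.1.1.1) | Named as a risk of Challenge (2.2.1.2.2) | Solicited from CHMI+7 (8.3.1.2) |
|---|---|---|---|---|---|
| Fever | 1.35 and 2.7 | 3 | yes | yes | yes |
| Chills | 1.35 and 2.7 | 3* | yes | yes | yes |
| Fatigue | 1.35 and 2.7 | 3* | yes | yes | yes |
| Myalgia | 1.35 and 2.7 | 3* | yes | yes | yes |
| Headache | 1.35 | 2 | yes | yes | yes |
| Arthralgia | 1.35 | 1 | yes | yes | yes |
| Sweats | 1.35 and 2.7 | 3* | **no** | yes | yes |
| Vomiting | 2.7 | 3* | **no** | yes | yes |
| Diarrhea | 1.35 | 1 | **no** | yes | yes |
| Abdominal pain | 1.35 | 1 | **no** | yes | yes |

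*If Grade 3 in that sentence governs every symptom in it; it certainly governs fever.

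Coverage: 6 of 10 listed, 10 − 6 = 4 omitted.

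**Step 2: participants.**
- Reactors: 4 (of 6) + 1 (of 6) = 5 of 12 in the two higher-dose groups.
- With at least one solicited symptom: all 4 in the first group had headache, and the 1 in the second had fever, chills, myalgia and fatigue. Total 5/5.
- At Grade 2 or above: 2 (headache) + 1 (Grade 3 fever) = 3, each reaching that grade on a solicited symptom. Total 3/3.
- With omitted symptoms only: 0/5. Exact one-sided 95% upper bound: 1 − 0.05^(1/5) = 0.45.

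**Step 3: this trial's dose.** Reactions 0/6. Exact one-sided 95% upper bound: 1 − 0.05^(1/6) = 0.39. The absence is reassuring, but six people cannot settle the question.

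**Step 4: the endpoint.** The synopsis counts related solicited and unsolicited events of at least moderate grade, or serious, plus laboratory abnormalities. Section 3.2 counts related solicited and unsolicited events with no grade limit. On either wording the four symptoms are eligible through the unsolicited route. Under the synopsis threshold, Grade 1 diarrhea and abdominal pain would not count even if solicited.

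**Step 5: effect of adding the four.** Symptom coverage rises from 6/10 to 10/10. The participant counts for the known signal stay at 5/5 and 3/3.

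**The case against.** The strongest reply is that nothing in the primary comparison is lost. The endpoint includes unsolicited events, and Section 9.4.4 compares event rates between arms by Fisher's exact test. Every known reactor is counted on a symptom already listed. The open question is put to the participant after the list is reviewed, and adverse events are updated at visits 2 and 7 days after dose 2 (Section 8.1.4), so a reaction beginning 10 to 24 hours after the dose would be recent. The malaria list is longer because it covers expected signs of malaria. The list of events in Section 2.2.1.1.3 is pooled and varied by trial. All of this stands, and it limits the point to symptom-level description.

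A reader might infer that vomiting with diarrhea would be recorded as an intercurrent illness and drop out as unrelated. The documents do not establish that. Section 8.3.5 allows individual symptoms to be recorded when no diagnosis is possible. Section 8.3.3.2 rates an event with reasonable timing as possible even if another cause is likelier, and possible counts as related.

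The reply does not explain the omission. Section 2.2.1.2.2 is not a malaria list: it names all four as vaccine-type reactions in the days before malaria could appear, yet the same short list is used in those days.

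**Conclusion.** The omission is real and unexplained, and its effect is modest. Four of the ten symptoms in the only symptomatic second-dose signal are left to a less sensitive route of collection. That weakens their individual rates and the solicited systemic total. The participant-level count of the known signal is unchanged. This assumes that future reactors resemble the five described, with at least one listed symptom each; five people cannot exclude a sizeable share with omitted symptoms only (upper bound 45%).

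Three stronger readings are tempting and unsupported. First, that the primary tolerability comparison rests on a partial list: it does not, because unsolicited events count. Second, that the trial loses a stated amount of power: that would need assumed symptom rates and capture shares, and a stand-alone test of these four symptoms, none of which the documents provide. Third, that participants are not told of these reactions: Section 2.2.1.1 only describes the consent list, and the form itself is not among the documents reviewed.

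The word symptomatic matters, because lymphocyte decreases followed the second dose in all groups, including the one at this trial's dose.

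**What to change.** Add sweats, nausea/vomiting, diarrhea and abdominal pain to the solicited systemic events in Sections 8.1.4 and 8.3.1.1.1 and to the memory aid, for 7 days after each vaccine or saline dose. Use the same list from CHMI to CHMI+6, so that it runs on into the malaria list at CHMI+7. Bring the solicited list described at the end of Section 2.2.1.1 into line. If the sponsor prefers the shorter list, the protocol should give the reason.

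The cost is four rows on the memory aid and the solicited event form, in terms that the post-CHMI form already uses. Some background gastrointestinal complaints will be recorded in both arms; the blinded saline arm accounts for these. No change to sample size or to the planned tests is needed.
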